### Non-technical summary:

Although serious complications from second trimester abortion are rare hemorrhage is the most common cause of procedural abortion related morbidity and mortality (Zane et al., 2015). Misoprostol is a prostaglandin E1 analogue that is used by 75% of clinicians (White et al., 2018) prior to procedural abortion for the purpose of cervical preparation. Misoprostol is also known to decrease blood loss in first trimester abortion and is used to treat postpartum hemorrhage, however the effect of preprocedural misoprostol on second trimester abortion blood loss is not well described.

We will conduct a double blinded placebo-controlled gestational age stratified superiority trial of those undergoing procedural abortion between 18 and 23 weeks gestation at Stanford Health care. Participants will be randomized to either 400mcg buccal misoprostol or placebo on the day of the procedure. A quantified blood loss (QBL) will be measured during the procedure and participants will complete a survey to assess symptoms. Our primary outcome is quantified blood loss. Secondary outcomes include clinical interventions to manage excess bleeding, total procedure time, provider reported experience, patient reported experience. We plan to recruit 80 subjects powered to detect a 30% reduction in QBL in those who received misoprostol compared to the control group.

This study has the potential to increase the safety of an already safe procedure and establish clinical benefits of choosing misoprostol as an agent for cervical preparation.

#### **Specific Aims:**

Primary aim:

To investigate the impact of administering 400 micrograms of buccal misoprostol 90-120 minutes prior to second trimester procedural abortion on quantified blood loss.

# Secondary aims:

Patient experience: evaluate the subjective experiences of patients who receive misoprostol before second trimester abortion focusing on pain before and after administration of the treatment, side effects, and overall satisfaction with the experience.

Procedure: analyze whether the use of misoprostol prior to second trimester abortion influences the procedure times, ease of procedure, provider estimated blood loss, provider satisfaction with cervical preparation, and whether the clinician could tell whether misoprostol was used.

# **Background and Significance:**

The definition of hemorrhage in second trimester abortion varies across studies with some focusing on volume of blood loss whereas others focus on clinical outcomes or interventions related to blood loss. Given these variable definitions the incidence of hemorrhage ranges from 0.9 to 10 per 1000 cases (Altman et al., 1985; Castleman et al., 2006; Frick et al., 2010; Patel et al., 2006; Schulz et al., 1985).

Clinical guidelines from the Society of Family Planning (SFP) recommend adequate cervical preparation and to consider vasopressin in a paracervical block to prevent hemorrhage for all patients (J. Kerns & Steinauer, 2013). The same guidelines outline management of hemorrhage including uterine massage, uterotonic medications, re-aspiration, balloon tamponade, uterine artery embolization, and hysterectomy. A randomized controlled trial (RCT) in 2019 by Whitehouse et. Al. examined the effects of prophylactic oxytocin on blood loss during procedural abortion 18-24w duration with primary outcome of frequency of interventions to control excess bleeding (Whitehouse et al., 2019). While prophylactic oxytocin did not decrease interventions needed to control excess bleeding, it did decrease hemorrhage (defined as blood loss of 500mL or more) by 18% (95% CI -29 to -6.9) and median blood loss by 165mL (152mL in oxytocin group [interquartile range 98-235] versus 317mL [interquartile range 168-464; 95% CI 71.6-181.5]). Another RCT by Kerns in 2021 examined the effects of prophylactic intramuscular methylergonovine for people undergoing procedural abortion 20-24 weeks (J. L. Kerns et al., 2021). They found no improvement in the composite of indicators of excessive blood loss with a paradoxical increase in the number of individual excessive bleeding outcomes for the group that received methylergonovine.

Misoprostol is a synthetic prostaglandin E1 analogue that is used in gynecologic, obstetric, and abortion care to induce uterine contractions and for cervical softening (Allen & O'Brien, 2009). It has been shown to overall decrease estimated blood loss in first trimester procedural abortion (Ngai et al., 1995, 1999; Saxena et al., 2003; Vimala et al., 2003) and is used to treat postpartum hemorrhage ("Practice Bulletin No. 183: Postpartum Hemorrhage," 2017). Cervical

preparation is required prior to second trimester procedural abortion and can be broadly understood in two different categories: mechanical and pharmacologic. Mechanical methods of cervical preparation include inserting osmotic dilators (Dilapan-S or laminaria tents) or transcervical balloons (foley balloon or Cook balloon). Pharmacologic methods of cervical preparation include mifepristone, misoprostol, and ulipristal acetate. Misoprostol is commonly used as part of cervical preparation for second trimester abortion (Diedrich et al., 2020; Fox & Krajewski, 2014) with 75% of clinicians report using misoprostol (White et al., 2018) it has not been shown to be a superior method of cervical preparation nor has it shown to improve clinical outcomes. The impact of use on procedural blood loss has not been consistently described (Cahill et al., 2020). Studies that do report on blood loss tend to use estimated blood loss which has been shown to consistently underestimate blood loss when compared to a measured blood loss (Serapio et al., 2018). Some clinicians do not use misoprostol out of concern for unpleasant side effects, how the procedure is then performed, and impact on procedural times (Drey et al., 2014). Further studies examining the specific effects of misoprostol on blood loss could help to better inform clinicians on the impact of misoprostol for cervical preparation on bleeding with second trimester procedural abortion.

# **Project Design and Methods:**

Study Location

Patients will be recruited at Stanford Gynecology Clinic in Palo Alto, CA. Stanford University is a large tertiary care center with patients referred from the seven Perinatal Diagnostic Centers (PDCs) across Northern California with fetal anomalies as well as local independent clinics.

#### Research Design and General Methodological Approach

The proposed study is a conduct a randomized, double-blinded, placebo-controlled, superiority trial. Participants will be consented and randomized using a computer-generated random number producing algorithm to receive either misoprostol 400mcg or placebo, buccally 90-120 minutes prior to their scheduled procedure time. Pharmacy staff filled identical, opaque pill containers with either two 200mcg misoprostol tablets or two 50-mg vitamin B6 tablets (placebo) because no identical appearing placebo exists for misoprostol. To ensure blinding of research and clinical staff subjects will self-administer study tablets in private where a research assistant who is uninvolved with collection of data will be available to assist patients with correct buccal placement. All other clinical and research staff will be blinded to the study group assignments until data analysis is complete.

The primary outcome will be proportion of participants with blood loss (QBL) above published medians by gestational duration(Serapio et al., 2018). To detect a 30% reduction in the proportion of participants with QBL greater than the median, with an alpha of 0.05 and a power of 80%, we would need 36 participants per group. Accounting for drop out, loss to follow up, and missing data, we plan to recruit 40 per group, for a total of 80 participants. With an estimated 180 procedures per year, 80% eligible, and 60% enrollment, we estimate the study will take 12-15 months to enroll. QBL will be measured using previously published protocols(Serapio et al., 2018). QBL was selected as the primary outcome because the incidence

of hemorrhage in second trimester abortion is a rare outcome. Lower QBLs correspond to lower risks and rates of hemorrhage therefore QBL may be a reasonable proxy to understanding morbidity and mortality related to procedural second trimester abortion.

Secondary outcomes will include clinical intervention to manage excess bleeding (use of uterotonics, uterine artery embolization, uterine balloon tamponade, blood transfusion, hysterectomy), total procedure time, provider-reported experience (ease of procedure, provider estimated blood loss, provider satisfaction with cervical dilation, and whether the clinician accurately predicted which treatment arm the subject was in), participant-reported experience (pain, side effects: nausea, vomiting, diarrhea, fevers), preoperative exam for dilation, need for mechanical dilation. Patient and provider experience are important outcomes to consider as some providers specifically chose methods of cervical preparation based on patient experiences and based on the way that the provider themselves perform the procedure. Because there is no one standard way to prepare cervices for second trimester procedural abortion providers choose methods of cervical preparation that they are most comfortable and familiar with based on how it changes the way they perform the procedure itself and how patients tolerate the various methods of cervical preparation. For example, pharmacologic preparation with misoprostol may cause side effects such as nausea, diarrhea, and fever, whereas osmotic dilators may cause more pain with placement and more pain overnight prior to procedure.

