Misoprostol Effect on Second Trimester Abortion Blood Loss

Statistical Analysis Plan

NCT06078501

August 23, 2023

To detect a 30% reduction in the proportion of participants with quantitative blood loss (QBL) greater than the median, with a two-sided alpha of 0.05 and 80% power, we calculated that 36 participants per group would be needed. To allow for attrition, we planned to recruit 40 participants per group, for a total of 80 participants.

Descriptive statistics will be used to summarize baseline characteristics. Continuous variables will be compared using t-tests or Wilcoxon rank-sum tests, depending on distribution. Categorical variables will be compared using chi-square or Fisher's exact tests. Multivariable logistic regression was used to estimate the association between treatment group and the primary outcome (QBL greater than the median), adjusting for potential confounders.

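### The primary outcome reduces measured blood loss to above or below a published median with no stated clinical reason; a rank test on the volumes would gain roughly 2 to 14 points of power at no cost in patients

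*Protocol*

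**What the plan says.** The Protocol (Research Design and General Methodological Approach) defines the outcome as a proportion: "The primary outcome will be proportion of participants with blood loss (QBL) above published medians by gestational duration". It sizes the trial on that proportion: "To detect a 30% reduction in the proportion of participants with QBL greater than the median, with an alpha of 0.05", and then "a power of 80%, we would need 36 participants per group". Recruitment is set above this for attrition: "we plan to recruit 40 per group, for a total of 80 participants". The SAP repeats the calculation, makes it two-sided ("with a two-sided alpha of 0.05 and 80% power, we calculated that 36 participants per group would be needed"), and names the model: "Multivariable logistic regression was used to estimate the association between treatment group and the primary outcome (QBL greater than the median").

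Other parts of the Protocol point to the volume itself. The primary aim under Specific Aims is "To investigate the impact of administering 400 micrograms of buccal misoprostol 90-120 minutes prior to second trimester procedural abortion on quantified blood loss". The Non-technical summary names quantified blood loss as the primary outcome and gives the powered effect as a 30% fall in QBL, not in a proportion.

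No analysis of QBL in mL is named as primary, secondary or sensitivity. The Protocol's list of secondary outcomes omits it. The SAP's general rule for continuous variables (t-test or Wilcoxon, by distribution) could cover it but does not mention QBL.

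**The concern.** QBL will be measured as a volume in each participant, but the primary test uses only which side of a published median it falls on. Two participants far apart in mL count the same if both are above the cut, and two a few mL apart count as different if they straddle it.

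The design section explains why QBL was preferred to haemorrhage: haemorrhage is rare, and lower QBL goes with lower risk. That is a graded argument, and it supports analysing the volume. Nothing in either document presents a median as a clinical threshold or cites a requirement for one.

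Two things are at stake. One is power in a trial of 80 people. The other is the form of the answer: a proportion above a median does not say how much blood loss changed.

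**Working it through.** **Inputs.** From the documents: 36 evaluable per group, two-sided alpha 0.05, 80% power, a 30% reduction in the proportion above the cut. Not in the documents: the control proportion (taken as 50% because the cut is "above published medians by gestational duration") and the distribution of QBL in this population. The only shape information is in Background and Significance, for one oxytocin trial: median 317 mL (IQR 168-464) without oxytocin and 152 mL (98-235) with it.

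**1. The plan's figure.** With 50% versus 20% and unpooled variance, n = (0.25 + 0.16) × (1.960 + 0.842)² / 0.30² = 35.8, so 36 per group. A relative reading (50% to 35%) gives 167-170 and does not reproduce. The plan's effect is therefore taken as 50% versus 20%.

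**2. Power of the cut at 36 per group.** Same formula: 0.30/√(0.41/36) − 1.960 = 0.851, giving 80.3%. The pooled formula gives 77.2%, simulated chi-square about 79%, and Fisher's exact test about 70%.

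**3. The same effect on the volume scale.** If log QBL is normal with equal spread, 50% to 20% is a shift of 0.842 SD. The noncentrality is 0.842 × √(36/2) = 3.57, and the t-test has 94.1% power. Wilcoxon has about 93%.

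**4. Is log-normality supported?** In the arm without oxytocin, the distances from median to quartiles are 149 and 147 mL, almost symmetric in mL. On the log scale they are ln(317/168) = 0.63 below and ln(464/317) = 0.38 above, which is left-skewed. The oxytocin arm is log-symmetric (0.44 and 0.44). The implied log SDs differ: ln(464/168)/1.349 = 0.75 and ln(235/98)/1.349 = 0.65. Three quantiles do not fix a distribution, so several shapes were tried.

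**5. Power at 36 per group, always 50% versus 20% above the cut.** These are simulations; with 8,000 runs the standard error is about √(0.8 × 0.2/8000) = 0.4 point.

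| Assumed shape | Cut, chi-square | Wilcoxon | t-test on log QBL |
|---|---|---|---|
| Log-normal, equal spread | 79% | 93% | 94% |
| Log QBL heavy-tailed (t, 4 df) | 79% | 89-90% | 80% |
| Gamma, shape 2.2 | 79% | 88% | 86% |
| Weibull, shape 1.6-1.9 | 78-79% | 85% | 78-79% |
| Control normal in mL around the quartiles above, truncated at 10-30 mL, multiplicative effect | 79% | 81-83% | 67-76% |
| Same control, treated arm log-normal (log SD 0.648) | 79% | 81-83% | 64-75% |

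Other symmetric shapes for log QBL (logistic, Laplace, t with 3 df) gave Wilcoxon gains of 9-12 points. A right-skewed log scale (Gumbel) gave 19, but neither set of quoted quartiles points that way. In every shape tried, Wilcoxon did at least as well as the cut; the log-scale t-test did not.

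**6. What 36 per group can detect on the volume scale.** With a t-test on log QBL, 80% power needs a shift of 0.670 SD. At log SD 0.65-0.75 that is a reduction of 1 − exp(−0.670 × 0.65) = 35% to 1 − exp(−0.670 × 0.75) = 40%. The rank test needs slightly more. The 30% reduction in the Non-technical summary is −ln(0.7)/SD = 0.357/0.75 = 0.47 to 0.357/0.65 = 0.55 SD. Power for it is about 50-63% on the full scale and about 35-44% with the cut.

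**The case against.** The plan meets its stated 80% on the formula that yields 36, so there is no arithmetic error. That stands: this is lost efficiency, not a broken calculation.

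The gain depends on a shape that nobody has established, and the Protocol's own control quartiles do not look log-normal. That also stands. It limits the size of the claim and rules out a log-scale model as the primary test, but it does not reverse the direction for ranks.

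The cut allows for gestational duration. It does, but stratifying a rank test by gestational age does so too and keeps the volumes.

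The volumes are not necessarily thrown away. The SAP's rule for continuous variables could be applied to QBL, and the Non-technical summary already names QBL as primary. Reconciling the documents towards that summary would largely settle this point. As written, though, the sample size and the named model both rest on the proportion.

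A reader might infer that power must fall further if fewer controls at this site exceed the published medians. That holds only if the true shift in SD units is fixed: at control rates of 35% or 25% the cut then has about 70% or 61% power. If the 30-point drop is fixed instead, 35% versus 5% gives about 91%. The documents do not say which quantity to hold fixed, so this is not a separate fault.

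**Conclusion.** The point holds as an efficiency and coherence problem. A measured volume is dichotomised without a clinical reason, against the stated aim and the Non-technical summary. For the effect that reproduces 36 per group, a Wilcoxon test on QBL has about 81-93% power against about 79% for the cut. The gain is about 2-5 points if control QBL is near-symmetric in mL, as the quoted control quartiles suggest, and up to about 14 if QBL is log-normal with equal spread. This rests on an inferred 50% control rate and on assumed shapes.

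A reader might take 15 points as the cost of the cut, or conclude that it makes a missed effect three to four times as likely (about 21% against 6%). Those figures are the favourable end. They require log-normality with equal spread, which the documents do not support. Under shapes built on the quoted control quartiles, a log-scale t-test drops to 64-76%, below the cut.

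Nor does moving to the volume scale deliver the Non-technical summary's 30% reduction: power for that is only about 50-63% at log SD 0.65-0.75.

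**What to change.** In the Protocol's design section and the SAP, make QBL in mL the primary outcome, in line with the Specific Aims and the Non-technical summary. Compare arms by a Wilcoxon rank-sum test stratified by gestational age (van Elteren), and report a Hodges-Lehmann median difference with 95% CI. Use the strata that the trial randomises by. The Non-technical summary calls the trial stratified by gestational age but no section defines the strata, so they need to be written down.

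Keep regression of log QBL (ratio of geometric means) as a sensitivity analysis and the proportion above the published median as a secondary outcome.

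Keep 80 participants. Restate what 36 per group can detect: roughly a 35-40% reduction with 80% power under log-normal QBL with log SD 0.65-0.75, slightly more for the rank test. Say openly that a 30% reduction has only about 50-63% power.

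The cost is revised wording and a changed primary outcome definition, with no new data, visits or participants. Changing a primary outcome is more than editing: it must be dated and completed before unblinding. The SAP mixes past and future tense, so the trial's stage should be stated alongside. The headline result becomes a difference in blood loss instead of a proportion.

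### The 30% in the power statement matches 36 per group only as a drop from 50% to 20%, and the summary's claim of power for a 30% fall in blood loss is not supported

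*Protocol*

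**What the plan says.** The protocol (Research Design and General Methodological Approach) defines the primary outcome as the "proportion of participants with blood loss (QBL) above published medians by gestational duration". It gives the sample size basis as "To detect a 30% reduction in the proportion of participants with QBL greater than the median", with alpha 0.05 and 80% power, and concludes that "we would need 36 participants per group". This is raised to 40 per group for attrition. The SAP gives the same basis, "To detect a 30% reduction in the proportion of participants with quantitative blood loss (QBL) greater than the median", and adds that alpha is two-sided.

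The protocol's Non-technical summary describes the same sample differently: "We plan to recruit 80 subjects powered to detect a 30% reduction in QBL in those who received misoprostol".

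On analysis, the SAP says "Categorical variables will be compared using chi-square or Fisher's exact tests". For the primary outcome it adds "Multivariable logistic regression was used to estimate the association between treatment group and the primary outcome (QBL greater than the median"), with adjustment for confounders that it does not name. No passage gives a control rate, a misoprostol rate, the scale of the 30%, or the test behind the 36.

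**The concern.** One sample size is attached to two different effects: a change in the share of participants above a cut-off, and a fall in a volume. They are not interchangeable. How far the share moves when blood loss falls by 30% depends on how spread out blood loss is, and the power statement does not use that spread.

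The proportion statement can itself be read in two ways, which differ more than fourfold in the sample size they need. A reader who takes 30% as relative, or who relies on the summary, will think the trial can detect a considerably smaller effect than the one that reproduces 36. A null result could then be taken as evidence against effects for which the trial did not have 80% power.

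**Working it through.** **Inputs.** Two-sided alpha 0.05 (SAP), 80% power and 36 per group (both documents), 1:1 allocation. The control rate is not stated. I assume 50%, which is natural for a median cut-off; but the medians are external, so the placebo rate here could differ.

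**1. Reproduce 36.** The unpooled formula is n = (1.96 + 0.8416)² × (p1q1 + p2q2) / (p1 − p2)², where the squared term is 7.849.

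- 50% to 20%: 7.849 × (0.25 + 0.16) / 0.09 = 35.8, so 36. The pooled formula gives 39. This is 30 percentage points, or 0.30/0.50 = 60% relative.
- 50% to 35%: 7.849 × (0.25 + 0.2275) / 0.0225 = 166.6, so 167. The pooled formula gives 170.

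Arcsine, continuity-corrected and one-sided versions do not bring the relative reading near 36; the lowest is 131. A 30% relative reduction needs only 36 per group if the control rate is about 89-91% (95% with continuity correction), which is implausible for a share above a median. Attrition: 36/0.90 = 40, so about 10% is implied.

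**2. Exact power of the unadjusted test**, by enumerating all 2×2 tables (40 per group applies only if nobody is lost):

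| Effect on the proportion | Chi-square, 36 | Fisher, 36 | Chi-square, 40 | Fisher, 40 |
|---|---|---|---|---|
| 50% to 20% | 79% | 70% | 82% | 75% |
| 50% to 35% | 24% | 17% | 29% | 21% |

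For a 30% relative reduction from control rates of 30% to 70%, power at 36 is 14-44% with chi-square and 9-34% with Fisher.

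**3. The summary's claim, carried to the primary outcome.** This needs the spread of blood loss, which the plan does not give. The only figures available are quartiles from a cited oxytocin trial (Background and Significance): "152mL in oxytocin group [interquartile range 98-235] versus 317mL [interquartile range 168-464". They are not data from this trial.

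After a 30% fall, the share still above the control median equals the control share above median/0.7.

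- *Comparison arm, from the upper half.* 317/0.7 = 453 mL, just below the upper quartile of 464 mL. Linear interpolation gives 50% − 25% × (453 − 317)/(464 − 317) = 26.9%. A log-normal upper half has log-SD ln(464/317)/0.6745 = 0.565, so the share is Φ(ln 0.7/0.565) = 26.4%.
- *Log-normal, whole interquartile range.* Oxytocin arm: ln(235/98)/1.349 = 0.648, share 29.1%. Comparison arm: ln(464/168)/1.349 = 0.753, share 31.8%.

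| Share after a 30% fall in QBL | Chi-square, 36 | Fisher, 36 | Chi-square, 40 | Fisher, 40 |
|---|---|---|---|---|
| 26.4% | 55% | 44% | 60% | 50% |
| 26.9% | 53% | 42% | 58% | 48% |
| 29.1% | 44% | 34% | 49% | 40% |
| 31.8% | 35% | 25% | 39% | 31% |

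Sensitivity: chi-square power at 36 is 65% at log-SD 0.5 and 21% at log-SD 1.0. It reaches 80% only at a log-SD of about 0.42 or below.

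**4. The reverse question.** The fall in QBL that takes the share to 20% is 1 − exp(−0.8416 × log-SD): 38% at 0.565, 42% at 0.648 and 47% at 0.753.

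**The case against.** **The proportion statement is not wrong.** For an outcome that is a proportion, a 30% reduction can mean 30 percentage points, and on that reading with a 50% control rate the 36 comes out. This stands. The design section and the SAP are ambiguous, and they agree with each other. A reader might infer that the sample size was miscalculated; the documents do not support that.

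**The summary is for lay readers.** Its wording may be shorthand for the design section. That may explain it, but a 30% reduction in QBL cannot be read as percentage points of a proportion, and it is offered as the effect the trial is powered for.

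**The power figure for a fall in QBL rests on borrowed spread.** This also stands. The quartiles pool 18 to 24 weeks, whereas the outcome uses medians by gestational duration, so spread within gestational-age groups may be smaller and power higher. One end of the range uses an oxytocin-treated arm. The comparison arm is not symmetric on the log scale (lower half 0.94, upper half 0.56), and only the upper half matters here, which favours the higher end of the power range. A reader might conclude that the trial would more likely miss than find a 30% fall in QBL. The figures do not support that: the upper-half calculation gives chi-square power slightly above one half. What they support is power below 80%.

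**Conclusion.** The point holds in two parts.

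First, the effect in the design section and the SAP is under-specified. At a 50% control rate (assumed), 36 per group corresponds to 50% to 20%, a 60% relative reduction, with exact power of 79% (chi-square) or 70% (Fisher). It does not correspond to a 30% relative reduction at any plausible control rate.

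Second, the summary's power claim is wrong as written. It names a quantity other than the primary outcome. On the only spread figures in the documents, a 30% fall in QBL has roughly 35-55% chi-square power at 36 per group and 39-60% at 40. This second range depends on another trial's quartiles and on the assumed shape of the distribution. The mismatch between the two stated effects needs no assumption.

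Nothing here shows that 36 is wrong or that more participants are needed for the effect that reproduces it. The power of the adjusted logistic model cannot be computed, because its covariates are not named.

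**What to change.** - **Design section and SAP:** replace the 30% reduction with the control and misoprostol rates actually assumed. If that was the intention, say: from 50% to 20%, 30 percentage points, a 60% relative reduction. Name the test the power refers to and give its power at 36 analysable per group. Say how this relates to the logistic regression named for the primary outcome.
- **Non-technical summary:** replace the claim about a 30% reduction in QBL with the same statement.
- **If the sponsor intended a 30% relative reduction or a 30% fall in QBL:** the stated 80% does not hold, and the power for that effect must replace it.

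The cost is wording in three places and one confirmation by the sponsor of the rates used, with no change in sample size. The drawback is that the declared detectable effect will look less favourable.
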